Study Protocol and Statistical Analysis Plan

**Short-term Effects of Bowel Preparation on Gut Microbiome in
Patients Undergoing Endoscopic Colon Polypectomy**

China-Japan Friendship Hospital

Department of Gastroenterology

December 1, 2022

I. Background of the study

Good and adequate bowel preparation is essential for performing colonoscopy, especially for patients requiring endoscopic treatment, and the role of bowel cleansing agents (i.e., laxatives) and their safety for patients have been extensively studied [1]. A variety of laxatives are used in clinical practice, the most widely used being electrolyte-supplemented polyethylene glycol (PEG) [2], a PEG solution that rapidly passes through the gastrointestinal tract causing severe osmotic diarrhea, altering the contents of the intestinal lumen, including the microbiota [3]. In addition, other types of laxatives have been developed, such as compounded sodium picosulfate granules, which stimulate peristalsis of the intestinal mucosa and act as an osmotic laxative, increasing the water content of the intestinal lumen, and are taken with a slightly better taste than PEG.

When a large amount of laxative passes through the gut, many microorganisms are removed from the gut. This results in significant changes in the composition of the gut microbiota during the intestinal cleansing process. A number of studies have been reported on the changes in the gut microbiome produced after gut cleansing in healthy populations [4-8] to assess whether gut cleansing directly leads to dysbiosis, whether the flora is restored, and to explore the impact of this process on health and disease. However, there is no consensus on how gut cleansing affects the gut microbiome. Some studies have found an increase in the relative abundance of Bacteroidetes and Ascomycetes and a decrease in the relative abundance of Thick-walled Bacteroidetes following gut cleansing [4, 9], however, others have found that gut cleansing does not have a significant effect on the microbiome [3, 7].

Colon polyps are a common gastrointestinal tumor, and most of these lesions are histologically adenomatous, with a risk of becoming cancerous [10], showing an "adenoma-adenocarcinoma" progression, so complete resection is essential. In most patients, polyps can be completely removed at an early stage by endoscopic mucosal resection (EMR) or endoscopic submucosal dissection (ESD) to avoid progression to colon cancer [11].

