There are still no studies reporting the effects of laxatives on the gut microbiome of patients with colon polyps, and in addition, most of the current studies, focusing on the effects on the gut microbiome after bowel cleansing with PEG [4, 7, 8, 12], have not explored whether other types of laxatives have different effects on the human gut microbiome. In our study, we plan to focus on different types of laxatives and explore whether they have different effects on the gut microbiome of patients with intestinal polyps after bowel cleansing, as well as to analyze whether the diameter of the colon polyps, pathological findings, and other baseline information also lead to different changes in the composition, evolution, and recovery of the gut microbiome of the patients, and to further explore the effects of microbiome changes on the patients' disease, and health.

II.Purpose of the study:

To investigate the role of different types of laxatives (compounded polyethylene glycol electrolyte dispersions and compounded sodium pico-sulfate) on the composition, evolution and recovery of the intestinal microbiome of patients with colonic polyps undergoing bowel preparation.

III.Overview of the study:

1. Study Steps:

Patients requiring e-colonoscopy and treatment for colon polyps were recruited and randomized into a polyethylene glycol group and a sodium picosulfate group. Patients in the two groups were prepared for bowel preparation with cotrimoxazole polyethylene glycol electrolyte dispersions and cotrimoxazole sodium picosulfate, respectively, while basic information about the patients was collected. Patients were left with feces before and after oral laxatives, and feces were left again 7 and 14 days after the end of intestinal cleansing, and intestinal microbiome sequencing was carried out to observe the changes in the intestinal microbiome of patients. The diameter of colonic polyps was recorded during the patients' operation, and the pathological results of colonic polyps were followed up after the operation.

2. Study population:

Patients who need to undergo electronic colonoscopy and treatment due to colon polyps.

3. Inclusion criteria:

- 1) All colon polyps diagnosed by electronic colonoscopy.
- 2) Age above 18 years old.
- 3) Patients sign an informed consent form, agree to cooperate with the study of this project, and collect fecal specimens on time to receive follow-up visits.

4. Exclusion criteria:

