Calculation of multiple Alpha diversity indices (richness, Chao1, Shannon, etc.) based on the (Z)OTU abundance table was performed using the USEARCH alpha_div subcommand (version 11.2.64). USEARCH beta_div was used to calculate the beta diversity distance matrices between samples, including weighted_unifrac, unweighted_unifrac and bray_curtis. Based on the three beta diversity distance matrices, PCoA analysis was performed and plotted using the R software, and based on the homogenization of OTUs. abundance table, PCA analysis was performed and plotted at different taxonomic levels using the gmodels package of R software, NMDS analysis was performed and plotted based on the three beta diversity distance matrices using the NMDS package of R software, and the three beta diversity distance matrices computed based on the homogenized OTU abundance table were analyzed and plotted using the Vegan package of R software (Version 2.4.2). Anosim analysis and mapping. Differential species composition was identified using DESeq2 (Version 1.26.0). Functional information in the samples was mined based on 16S sequences, mainly using the KEGG database of known bacteria and their functional annotation information for prediction. The investigators used the BLAST method to compare the (Z)OUT representative sequences with the SILVA_123_SSURef_Nr99 database to complete the sequence classification of the OTUs, and then used the Tax4Fun (version 0.3.1) package for R to obtain detailed abundance information of the KOs, and used the high level KEGG annotations of the metabolic pathways, enzymes, reactions, etc., which were associated with the KOs. information, and finally statistically analyzed and presented.

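### Four stools per patient are collected to study change and recovery, but no within-patient or baseline-adjusted analysis of the microbiome is named

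*Combined protocol and SAP*

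**What the plan says.** The purpose (section II) is to learn how the two laxatives act "on the composition, evolution and recovery of the intestinal microbiome". Under Study Steps (section III.1) the sampling is: "Patients were left with feces before and after oral laxatives, and feces were left again 7 and 14 days after the end of intestinal cleansing". The reason given there is that "intestinal microbiome sequencing was carried out to observe the changes in the intestinal microbiome of patients".

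Section IV then lists the microbiome methods:

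- **Alpha diversity:** "Calculation of multiple Alpha diversity indices (richness, Chao1, Shannon, etc.) based on the (Z)OTU abundance table was performed using the USEARCH alpha_div subcommand". No test is attached.
- **Beta diversity:** "USEARCH beta_div was used to calculate the beta diversity distance matrices between samples". The unit is the sample, and ANOSIM follows without a grouping factor or permutation scheme.
- **Differential abundance:** "Differential species composition was identified using DESeq2 (Version 1.26.0". No design formula, contrast, patient term or visit term is given.
- **Predicted functions:** to be analysed statistically, by a method that is not named.

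The SPSS paragraph of section IV is written for routine data. Its two-group tests (independent-samples t-test, Mann-Whitney U, chi-square, Fisher) all assume independent groups. No paired, mixed-model, repeated-measures or baseline-adjusted method appears anywhere, and recovery has no analysis definition.

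**The concern.** Evolution and recovery are questions about change within a patient, and the comparison of laxatives on them is an arm-by-visit question. The sampling schedule is built to answer them, but the analysis section does not say how the four stools of one patient are linked. Three ways of using the data are left open, with different consequences:

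1. **Compare the arms at one visit.** This is valid under randomization, but it says nothing about return to each patient's own starting point and ignores the baseline stool.
2. **Compare visits as if the samples were unpaired.** This is conservative and can miss a moderate shift.
3. **Pool visits to compare arms.** This counts correlated stools as separate patients and can produce false differences between laxatives.

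At stake is whether the trial can report on recovery, which is part of its stated purpose, and how much precision it gives away when the baseline stool is already in hand.

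**Working it through.** The documents give no sample size, alpha, effect size or within-patient correlation, so there is no figure of theirs to reproduce. All inputs below are assumptions except the four stools per patient (Study Steps): 20 patients per arm, two-sided alpha 0.05, unit-variance normal outcome, common correlation rho between a patient's stools. Triplets are for rho = 0.3/0.5/0.7. Closed forms use the normal approximation. Simulations use t-tests or analysis of covariance with 20,000 replicates, and run slightly below the closed-form powers because of the small sample.

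**Step 1. Arms compared at day 14, true difference 0.5 SD.**
- Single visit: 0.5 × sqrt(20/2) = 1.581; power = Phi(1.581 − 1.96) = 35%. Simulation: about 34% at every rho.
- Baseline-adjusted: the residual SD falls by sqrt(1 − rho²), so the signal is 1.581/sqrt(1 − rho²) = 1.657/1.826/2.214; power = 38/45/60%. Simulation: about 36/42/56%.

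The gain is small at rho = 0.3 and substantial at 0.7.

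**Step 2. Two visits compared in 20 patients, true shift 0.5 SD.**
- Paired: 0.5 × sqrt(20)/sqrt(2(1 − rho)) = 1.890/2.236/2.887; power = 47/61/82%. Simulation: about 44/56/78%.
- Unpaired: the test statistic has mean 1.581 but true variance only 1 − rho, so power = Phi((1.581 − 1.96)/sqrt(1 − rho)) = Phi(−0.453/−0.536/−0.692) = 33/30/24%. Simulation: about 31/28/25%.

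The loss shrinks with more patients or larger shifts. By simulation, at 80 patients and 0.5 SD power is 92/95/98% unpaired against 96/99/100% paired.

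**Step 3. What pooling would do, if it were done.** Treating four stools per patient as independent when comparing arms gives a true error rate of 2(1 − Phi(1.96 × sqrt((1 + v)/D))). Here D = 1 + 3 rho, and v is the variance of the visit means, which enters the pooled SD.
- No visit effect (v = 0): D = 1.9/2.5/3.1; false positives 15.5/21.5/26.6%. Simulation: about 16/22/27%. One mean per patient restores about 5%.
- Shared visit shifts of 0/−2/−0.5/0 SD: mean −0.625, v = (0.391 + 1.891 + 0.016 + 0.391)/4 = 0.672; false positives 6.6/10.9/15.0%.
- Same shifts, with the post-laxative stool uncorrelated with the other three: D = 1 + 1.5 rho = 1.45/1.75/2.05; false positives 3.5/5.5/7.7%.

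Inflation therefore ranges from large to almost none, depending on quantities that the plan does not give.

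**Step 4. A patient term in a DESeq2-type model.** A simplified check used a negative-binomial Wald test on one taxon, with no dispersion shrinkage, two visits, 20 patients and 1,000 replicates. At a nominal 5%, size was 3.1/0.9/0.3% without a patient term and 12.5/8.8/7.7% with one. This is not full DESeq2, but it gives no support for presenting a patient-term model as a safe default.

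**The case against.** The strongest reply is that this is silence, not a stated error. Section IV reads as a description of a sequencing pipeline, and both ANOSIM and DESeq2 can take patient structure if asked. The groups are the two randomized arms, so independent-sample tests with one value per patient are a natural reading, and a valid one. The aim is also exploratory: to "explore whether they have different effects on the gut microbiome of patients with intestinal polyps after bowel cleansing".

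Much of this stands. A reader might infer that the plan treats all stools as independent patients and so will inflate false positives. The documents do not support that: no sentence says visits will be pooled. Nor can the size of any inflation be fixed. The Background says of cleansing that "This results in significant changes in the composition of the gut microbiota during the intestinal cleansing process", and a shared shift of that kind reduces the inflation. The same section also reports no consensus and some studies without a significant effect, so the shift cannot be assumed either.

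The reply does not cover the stated aim. Even on the most favourable reading, one valid arm comparison per visit, no named analysis addresses change within patients or return to baseline. Being exploratory does not remove the need to say what is compared with what.

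**Conclusion.** The point holds as a gap in the analysis plan. Followed as written, the plan cannot show whether patients return to their own baseline, and it does not use the baseline stool to sharpen the comparison of laxatives. Under the assumptions above (20 per arm, 0.5 SD effects), baseline adjustment raises day-14 power from about 34% to 36/42/56%, and pairing raises visit-comparison power from about 31/28/25% to 44/56/78%. These figures are illustrations for a normally distributed index such as an alpha-diversity measure. They would change with the real sample size, correlation and effect. The pooling figures describe a risk that the wording leaves open, not an analysis that the plan prescribes. This is an inexpensive improvement, not a flaw that invalidates the trial.

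**What to change.** State in section IV that the patient is the unit of analysis, and add:

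- **Alpha indices:** compare arms at each post-laxative visit, adjusted for the patient's baseline value, or use a mixed model with a patient random intercept, visit and arm-by-visit. Report recovery as day 14 minus baseline with a 95% confidence interval, within each arm and as the difference between arms.
- **ANOSIM (Vegan, already named):** for visit effects, permute within patient. For arm effects, permute whole patients or use one value per patient, such as the distance from that patient's own baseline sample.
- **DESeq2:** compare arms at a single visit with one sample per patient. Label any model with patient terms as exploratory, because such a test was liberal in the simplified check (7.7 to 12.5% against a nominal 5%).

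The cost is a few sentences in the SAP and a little more analysis code. Samples, software and patient numbers stay the same.
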